4.4.2 Supportive Secondary Endpoints

4.4.2.1 Definition of Endpoints

- Time to reduction in required ventilator support to ≤ 16 hours a day (only in participants who require invasive ventilation) at Week 24
- Change from baseline in Children's Hospital of Philadelphia Infant Test of Neuromuscular Disorders (CHOP INTEND) at Week 24
- Change from baseline in maximal inspiratory pressure (MIP) at Week 24
- Change from baseline in quantitative analysis of myotubularin expression in the muscle biopsy at Week 24
- Change from baseline in quality of life assessments at Week 24 (ie, the Assessment of Caregiver Experience with Neuromuscular Disease [ACEND] and Pediatric Quality of Life Inventory [PedsQL])
- Number (%) of age-appropriate clinically relevant gross motor function milestones attained through Week 24
- Percentage of participants achieving full ventilator independence at Week 24
- Survival

4.4.2.2 Main Analytical Approach

The secondary efficacy analyses will be conducted for the FAS.

4.4.2.2.1 Time to reduction in required ventilator support to ≤ 16 hours a day (only in participants who require invasive ventilation) at Week 24

This endpoint will be summarized for low dose and the high dose groups separately in the participants who require invasive ventilation. Kaplan-Meier plots along with median (95% CI) time from the study start date to event will be provided.

The number of hours of ventilator support at each collected time point for this analysis will be taken directly from the daily diary (Protocol V5.0 and later) or by assessment of time off ventilator questionnaire (prior to Protocol V5.0). The first instance of time reduction reported as ≤ 16 hours per day will be considered an event. Participants will be censored at either Week 24 or withdrawal from study, whichever occurs first.

4.4.2.2.2 Change from baseline in Children's Hospital of Philadelphia Infant Test of Neuromuscular Disorders (CHOP INTEND) at Week 24

The change from baseline will be analyzed using the MMRM in a similar method to that used for the primary analysis of the primary efficacy endpoint, described in [Section 4.3.2](#).

Estimated change from baseline in CHOP INTEND score at Week 24 will be summarized by dose level.

In addition, the CHOP INTEND score and corresponding change from baseline at each visit will be summarized descriptively by dose level group.

The CHOP INTEND is an assessment scale that was originally designed to quantify motor abilities in infants aged 1.4 to 37.9 months, with spinal muscular atrophy type I (SMA-I) ([Glanzman, 2010](#)) and has been validated for XLMTM ([Duong, 2021](#)). The scale contains 16 questions, each of which is scored on a scale of 0 to 4, with 0 being no response/ability to perform the movement and 4 highest ability to perform the task, per CHOP INTEND item instructions.

The score used for analysis is the total sum of all 16 questions, which will range from 0 to 64. Higher score indicates better neuromuscular function. If an item is missing or scored as "Could Not Test (CNT)" then 0 will be imputed for the item score.

If a participant has 2 assessments with a total score of ≥ 56 , the CHOP INTEND will not be required for future visits.

Subject line plots of the CHOP INTEND over time will be created.

4.4.2.2.3 Change from baseline in maximal inspiratory pressure (MIP) at Week 24

The change from baseline will be analyzed using the MMRM in a similar method to that used for the primary analysis of the primary efficacy endpoint, described in [Section 4.3.2](#).

Estimated change from baseline in MIP at Week 24 will be summarized by dose level.

In addition, the MIP and corresponding change from baseline at each visit will be summarized descriptively by dose level group.

If a subject has discontinued the use of the ventilator and has 2 assessments with the MIP at 80 cmH₂O, testing for MIP, MEP, and P0.1 will not be required for future visits.

Subject line plots of the MIP over time by will be created.

4.4.2.2.4 Change from baseline in quantitative analysis of myotubularin expression in the muscle biopsy at Week 24

The change from baseline will be analyzed using the MMRM in a similar method to that used for the primary analysis of the primary efficacy endpoint, described in [Section 4.3.2](#).

Estimated change from baseline in myotubularin expression levels at Week 24 will be summarized descriptively by dose level.

In addition, the myotubularin expression levels and corresponding change from baseline at each visit will be summarized descriptively by dose level group.

Subject line plots of the muotubularin expression levels over time will be created.

These data will also be listed.

4.4.2.2.5 Change from baseline in quality of life assessments at Week 24 (ie, the Assessment of Caregiver Experience with Neuromuscular Disease [ACEND] and Pediatric Quality of Life Inventory [PedsQL])

The change from baseline will be analyzed using the MMRM in a similar method to that used for the primary analysis of the primary efficacy endpoint, described in [Section 4.3.2](#).

Estimaged change from baseline in the ACEND and PedsQL scores (described below) at Week 24 will be summarized descriptively by dose level.

In addition, the ACEND and PedsQL scores and corresponding change from baseline at each visit will be summarized descriptively by dose level group.

Subject line plots of the ACEND and PedsQL scores over time will be created.

ACEND

The ACEND was developed to measure impact on the lives of parents/legally authorized representatives (LARs)/caregivers caring for children with severe neuromuscular disorders ([Matsumoto, 2011](#)). Several domains of the ACEND (time, finance, and emotion) are relevant to assessing the caregiver burden of the parents of children with XLMTM.

ACEND contains 41 items which reflect 2 domains (physical impact and general caregiver impact). The physical impact domain includes 4 sub-domains: feeding/grooming/dressing (6 items), sitting/play (5 items), transfers (5 items) and mobility (7 items). The general caregiver impact domain includes 3 sub-domains: time (4 items), emotion (9 items), and finance (5 items). Score for each item is based on the 6- or 5-point ordinal scale, and scores for each domain and subdomain are scored on a scale of 0 - 100. Higher scores reflect

caregivers experiencing less intense care-giving impact. Sub-domain and total scores are thus meant to confer “impact health” in each caregiver respondent (Xu, 2020).

Raw scores for each subdomain are created by computing the algebraic mean of the items for those respondents who completed one item or more; setting missing for those items with no responses. Then, the arithmetic mean of the responded items is standardized to a 0 to 100 score using the following formula:

$$100 * \frac{\text{arithmetic mean of the items in subdomain} - 1}{\text{maximum item score in the subdomain} - 1}$$

Transformed scores should be 0 to 100 for each subdomain.

A total score can be calculated as the mean of the 7 subdomain scores. Domain scores will be calculated as the mean of the sub-domains. When any subdomain scores are missing, the total score (or domain score) will be missing. No items, subdomain scores, domain score, or total scores will be imputed.

Total scores and corresponding change from baseline will each be analyzed by MMRM as described above at Week 24 and summarized descriptively by dose level group and visit.

PedsQL

The PedsQL is a tool designed to measure health-related quality of life in healthy children and adolescents and those with acute and chronic health conditions. The PedsQL measures the core dimensions of health as delineated by the World Health Organization, as well as role (school) functioning. This questionnaire has different modules that are administered depending on the age and condition of the child.

The PedsQL neuromuscular module was designed to measure health-related quality of life dimensions specific to children aged 2-18 years with neuromuscular disorders and has been validated in other neuromuscular disorders such as SMA (Iannaccone, 2009). This is the module of the questionnaire that is used in this study, and is considered suitable to be used for children < 2 years of age.

Each item of the questionnaire is measured on a 5-point likert scale from – 0 (Never) to 4 (Almost always). The module is composed of 25 items comprising 3 dimensions:

- About My Neuromuscular Disease (17 items)
- Communication (3 items)
- About Our Family Resources (5 items)
- Total Scale Score

Higher scales/scores indicate lower problems.

Scores are derived in the following way:

- Step 1: Transform Score

- Items are reversed scored and linearly transformed to a 0-100 scale as follows: 0=100, 1=75, 2=50, 3=25, 4=0.
- Step 2: Calculate Scores by Dimensions x
 - If more than 50% of the items in the scale are missing, the scale scores should not be computed, $x \text{ Mean score} = \frac{\text{Sum of the items}}{\text{number of items answered}}$.
 - If more than 50% of the items in the scale are missing, the Scale Scores should not be computed.
 - If 50% or more items are completed: Impute the mean of the completed items in a scale.
- Total Score: Sum of all the items over the number of items answered on all the Scales.

Per protocol, the parent-report version of the questionnaire is supposed to be administered. In the case that the child-report version of the questionnaire is administered, the scoring algorithm will be adjusted accordingly.

Total scores and corresponding change from baseline will each be analyzed by MMRM at Week 24 as described above and summarized descriptively by dose level group and visit.

4.4.2.2.6 Number (%) of age-appropriate clinically relevant gross motor function milestones attained through Week 24

Protocol versions 1 to 4:

Bayley and motor milestone collection was intermittent and not required in versions 1 – 4 of the protocol, so data may be missing for some participants at some visits. In addition, the motor milestone eCRF was not added until version 5.0 of the protocol. As such, the Bayley III item (referenced in [Table 1](#)) corresponding to each motor milestone will be used for the analysis of the motor milestone data collected under protocol version 1 – 4. If the Bayley III result is not available for the visit, but the participant attended the visit, then their result will be included in the summary as “missing”.

Protocol versions 5+:

The motor developmental milestones listed in [Table 1](#) below will be derived in form of Yes (achieved) and No (not achieved).

Any motor milestone value that is collected prior to participants’ date of signing the informed consent for Protocol Version 5.0 will use the flowchart logic described in the “Protocol versions 1 to 4” section above for deriving the motor milestone achievement status. Records collected after that date will follow the logic corresponding to the “Protocol versions 5+” section.

Table 1 Motor Developmental Milestones

Development Milestone	Reference	Summary Description of Performance Criteria*	Expected Age of Achievement for Analysis (months)
Head Control	Bayley-III Gross Motor Subtest Item #9	Child holds head erect for at least 15 seconds without support	4.0†
Rolls from Back to Sides	Bayley-III Gross Motor Subtest Item #20	Child turns from back to both right and left sides	6.0†
Sits Without Support	WHO Multicentre Growth Reference Study	Child sits alone without support for at least 10 seconds	9.2^‡
Sits Without Support	Bayley-III Gross Motor Subtest Item #26	Child sits alone without support for at least 30 seconds	9.2^‡
Stands with Assistance	Bayley-III Gross Motor Subtest Item #33	Child supports own weight for at least 2 seconds	11.4^
Crawls	Bayley-III Gross Motor Subtest Item #34	Child makes forward progress of at least 5 feet by crawling on hands and knees	13.5^
Pulls to stand	Bayley-III Gross Motor Subtest Item #35	Child raises self to standing position using chair or other convenient object for support	12.0†
Walks with Assistance	Bayley-III Gross Motor Subtest Item #37	Child walks by making coordinated, alternating stepping movements. He/she may hold on with 1 or 2 hands for support.	13.7^
Stands Alone	Bayley-III Gross Motor Subtest Item #40	Child stands alone for at least 3 seconds after you release his or her hands.	16.9^
Walks Alone	Bayley-III Gross Motor Subtest Item #42	Child takes at least 3 steps without support, even if gait is stiff-legged and wobbly	17.6^

* See motor milestone manual for full description of performance criteria

† Per CDC. For the milestones covered by the CDC, the age at which >75% of children attained the milestone is used as the reference for analysis here.

^ Per WHO Multicenter Growth Reference Study (MGRS), 2006. For the milestones covered by the WHO MGRS, the upper bound of the range (1-99%) is used as the reference for analysis here.

‡ Duration of sitting in the reference (WHO Multicenter Growth Reference Study) is not clearly defined, so the same age is used for the expected age of achievement for both independent sitting milestones.

The number and percentage of participants achieving each gross motor function milestone will be summarized descriptively by low dose and high dose group by visit week through Week 24. A similar summary will be provided for visits occurring after Week 24.

The denominator of the percentage calculation will only include the participants who attended the visit and are expected to achieve the particular milestone based on their age (i.e., if at the time of an assessment the child is at least the age indicated in [Table 1](#), then they will be considered eligible for the milestone and will be included in the denominator). A child’s eligibility will need to be uniquely determined for each assessment at each time-point.

The denominator values will be included in the table.

The percent of age-eligible milestones that each participant achieves at Week 24 will also be summarized as a continuous (percentage) by visit and via shift table as an ordinal variable, by number and percent of participants in each category (None, at least 1, >1 to half of the expected milestones, >50% to <100% all expected milestones, All expected milestones) at baseline and shift post-baseline.

Number of age-eligible milestones expected at Week 24 (denominator for the calculation for the participant at the visit) is determined based on the age of the participant at the visit and the corresponding number of milestones expected for that age. The numerator of the calculation for the participant at the visit is the number of milestones that they have achieved. The corresponding percentage will be converted to the relevant category. The number of participants falling into each category regardless of age will be summarized at each visit.

Each participant's timeline of achieving the motor milestones will also be presented graphically.

Any assessment done prior to the date of the participant signing Protocol V 5.0 informed consent is assumed to correspond to protocol V1.0 – 4.0 data.

4.4.2.2.7 Percentage of participants achieving full ventilator independence at Week 24

“Full ventilator independence” is defined as: the date of removal from ventilator field on the “Assessment of Ventilator Parameters” eCRF is not blank or “Is subject on a ventilator” = “No” on the same eCRF.

The number and percentage of participants achieving full ventilator independence at Week 24 will be summarized descriptively by low dose and high dose groups.

In addition, a summary by visit week of the same parameter will be provided by dose level.

All ventilator parameter data will be listed.

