Following the occurrence of fatal serious AEs (SAEs) in Study ATX-MTM-002, the Sponsor, in consultation with the DMC and external experts, evaluated the data and reassessed the benefit/risk profiles of the 1.0×10^{14} vg/kg and 3.0×10^{14} vg/kg dose levels. As of the data cutoff date of 08 July 2020, 5 subjects who received 3.0×10^{14} vg/kg AT132 developed AT132-related SAEs involving the hepatobiliary system. In 2 subjects, these SAEs resolved; in 3 subjects, fatal events occurred subsequent to severe cholestatic liver dysfunction. Within the 3.0×10^{14} vg/kg dose level cohort, 8 of 17 subjects (47.1%) experienced 26 SAEs considered related to AT132. In contrast, within the 6 subjects dosed at the 1.0×10^{14} vg/kg dose level, all of whom are ≥ 2 years from AT132 administration, 1 (16.7%) subject experienced 4 AT132-related SAEs, all resolved, and none involved the hepatobiliary system. In addition to a favorable safety profile observed in the subjects treated with 1.0×10^{14} vg/kg, a clinically meaningful benefit continues to be observed in this group at last follow-up. In this group, which had a mean 20.5 hours (SE 2.02) of ventilation per day at baseline ($n = 5$ [83.3%] with invasive ventilation; $n = 1$ [16.7%] with non-invasive ventilation), 5 out of 6 (83.3%) subjects were ventilatory independent at last follow-up (as of data cutoff date 08 July 2020). With respect to gross motor development, at baseline 5 of the 6 subjects did not perform any of the following major motor milestones: sit unassisted for 30 seconds, raise self to standing position, stand alone, or walk alone. At baseline, 1 subject did sit unassisted for 30 seconds but did not perform the remaining motor tasks. At last follow-up following AT132 administration at 1.0×10^{14} vg/kg, 5 out of 6 subjects performed all of these motor tasks, including walking alone. Regarding performance on the Children's Hospital of Philadelphia Infant Test of Neuromuscular Disorders (CHOP INTEND), this 1.0×10^{14} vg/kg group demonstrated a baseline mean score of 37.7 (SE 2.42). At last follow-up, performance had improved to a mean score of 56.5 (3.97).

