3.7 Start and End of Study Definitions

First act of recruitment

The study start date is the date on which the clinical study will be open for recruitment of participants. The first act of recruitment is the date the first participant signs the informed consent form (ICF) and will be the study start date.

End of study

The end of the study is defined as the last visit or assessment shown in schedule of assessments ([Section 5.6](#)) for the last participant in the study. A participant is considered to have completed the study if the participant has completed all periods of the study including the last assessment shown in the schedule of assessments.

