4.3 Primary Endpoint Analysis

4.3.1 Definition of Endpoint(s)

The primary efficacy endpoint is change from baseline in hours of ventilation support at Week 24.

The hours of ventilation support will be based on diary data from participants for whom diary data was collected at baseline (those administered AT132 under protocol v5 and beyond, including all participants in Part 2), and by assessment of time off ventilator questionnaire for all other participants (those administered AT132 under protocol v4 and prior). Weekly scores will be the average of ventilation hours needed for at least 5 out of the 7 days leading up to and including the analysis visit day (e.g., Day 168 for Week 24). For cases where the diary or the ventilator assessment indicates that ventilator type = "None", then zero will be imputed for the number of hours on ventilator.

The days included for the average for the particular visit week are defined by $\text{avisit} = \text{"Week"} \parallel \text{strip}(\text{put}(\text{ceil}(\text{ady}/7), \text{best.}))$, where ADY = the analysis visit day of the diary entry.

If at least 5/7 days of the visit week are non-missing, then the remaining missing values will be ignored in the calculation of average ventilation hours needed. Otherwise, if <5 non-missing diary records are available for the visit week, then up to 4 missing values will be imputed by the worst score of the week (most hours on ventilator), so that at least 5 records are available for calculating the average for the week.

Baseline is defined as the average of the diary data values in the 7 days leading up to and including the day of administration of the study drug (i.e. Analysis Day – 6 through Day 1). The missing data approach described in the paragraph above will be used if <7 days of data are available at baseline. If only non-diary ventilator questionnaire data is available at baseline, the last record prior to administration of study drug will be used for the baseline value.

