4.4.2.2.8 Survival

This endpoint will be summarized for low dose and the high dose groups separately for all participants in the FAS. Kaplan-Meier plots of time from the dosing date to event will be provided. In addition, the estimated survival rate at the following time-points will be presented by dose level group:

- 3 months
- 6 months
- 1 year
- 2 years
- 5 years
- 10 years

For this analysis, the date of a participant's death is considered the time of an event. Survival status should be assessed at each visit until the participant withdraws consent or completes the study. If the participant misses a visit or withdraws for a reason other than withdrawal of consent or death, the site should contact the parent(s)/LAR(s) to ascertain if the participant is

alive. For participants who withdraw from the study, the participant should be contacted every 6 months for 5 years after administration and every year for an additional 5 years (after the 5-year follow-up through 10-years follow-up) to assess for survival. If not alive, the cause and date of death should be requested and recorded.

Participants will be censored at the last known date/time of contact.

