4.7.1.2 Biodistribution and Vector Shedding

All available vector DNA in muscle biopsy data and vector shedding data will be included in a participant listing.

Vector DNA in muscle biopsies will be summarized descriptively by visit and dose level group.

Maximum vector DNA concentrations (Cmax) and time to achieve maximum concentration in shedding matrices (Tmax) will be summarized descriptively by dose level group.

The duration of vector shedding will be summarized descriptively by dose level using Kaplan-Meier plots along with median (95% CI) and quartile time from the administration of study drug to event. Additional summary statistics will be provided for participants who are not censored.

The event of 'end of vector shedding' is defined as the date of the first of three vector shedding results measured as below the lower limit of quantification (LLOQ). Participants will be censored at the last known date/time of contact.

Spider plots of vector shedding data over time will be created by dose level group.

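### Time to ≤16 h/day ventilation and time to unassisted sitting are measured from the study start date (first participant's consent), not from each child's dosing

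*SAP*

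**What the plan says.** SAP 4.4.2.2.1 summarises time to ventilator support of 16 hours a day or less by dose, in invasively ventilated participants: "Kaplan-Meier plots along with median (95% CI) time from the study start date to event will be provided". SAP 4.5.1.2.1 uses the same sentence for time to unassisted sitting. Protocol 7.4.2.2.2 uses it for the ≤16 h endpoint, for a reduction of at least 6 hours, and for death.

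The SAP does not define the study start date. The only definition is in Protocol 3.7: "The first act of recruitment is the date the first participant signs the informed consent form (ICF) and will be the study start date".

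For the ≤16 h endpoint, SAP 4.4.2.2.1 adds: "Participants will be censored at either Week 24 or withdrawal from study, whichever occurs first". SAP 4.3.1 and Table 9 put Week 24 at Day 168, with dosing as Day 1.

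Elsewhere the SAP starts the clock at dosing. For survival (4.4.2.2.8): "Kaplan-Meier plots of time from the dosing date to event will be provided". For vector shedding (4.7.1.2): "median (95% CI) and quartile time from the administration of study drug to event".

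**The concern.** The written origin is a trial-level calendar date, while the quantity of interest is how long a child takes to respond after treatment. Measured from first consent, each time is the sum of an enrolment lag and a response time, and a later-dosed child looks slower whatever his response.

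The lag is tied to dose. Protocol 1.4.2 says the high-dose cohort opened only after all six Cohort 1 children had been dosed and reviewed. Low and high dose are the groups being described (SAP 1.3), so even with identical responses after dosing, high-dose children would appear slower than those six.

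The ≤16 h rule also mixes two clocks: its origin is study start, but its censoring point, Week 24, is counted from dosing.

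**Working it through.** The documents give no figure that depends on the origin, so there is none to reproduce. The size of the problem can be bounded from their dates.

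**Identity.** Time from study start = (dosing date − study start date) + time from dosing. The first term is the lag.

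**Inputs**
- At the 08 July 2020 cutoff, Protocol 1.4.2 describes the six low-dose children as "all of whom are ≥ 2 years from AT132 administration". All six were therefore dosed by 08 July 2018.
- Later members of a cohort were randomised only after at least 4 weeks (28 days) of post-dose data from the sentinel (Protocol 3.1).
- Protocol v1.0 is dated 22 February 2017 and v5.0 is dated 01 May 2019 (protocol version list).
- The response window is 168 days.

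**When was first consent?** The Cohort 1 sentinel was dosed by 08 July 2018 − 28 days = 10 June 2018, and first consent was no later than that. I take the v1.0 date as the earliest possibility.

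**Lag for any child dosed under v5 or later**
- At least 01 May 2019 − 10 June 2018 = 325 days (46 weeks; 325/168 = 1.9 windows).
- If first consent was as early as the v1.0 date: at least 01 May 2019 − 22 February 2017 = 798 days (798/168 = 4.75 windows).

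**Extra lag compared with any of the six Cohort 1 low-dose children**
- At least 01 May 2019 − 08 July 2018 = 297 days (42 weeks; 297/168 = 1.8 windows). The first-consent date cancels out of this difference.

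**Effect on the high-dose sitting curve (conditional).** Protocol 1.4.2 reports for the high dose that "8 of 17 subjects (47.1%) experienced 26 SAEs considered related to AT132", so 17 children had received it by that cutoff. Cohort 2 was 3 children plus 3 to 5 more, that is 6 to 8, which leaves 11 to 9 others. Assume all 17 are analysed and those others were dosed under v5 or later. SAP 4.3.1 places all Part 2 participants there, and the Figure 2 notes say Part 1 controls were treated after the therapeutic dose was chosen, a decision reflected in v5. Before day 325 only Cohort 2 children can have events, so the Kaplan-Meier curve cannot fall below 9/17 = 0.53 (Cohort 2 of 8) or 11/17 = 0.65 (Cohort 2 of 6). Censoring in Cohort 2 would raise that floor. The median would be at least 325 days even if every child responded the day after dosing.

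**Illustration with assumed values.** Individual dosing and event dates are not given. I simulated 6 low-dose and 17 high-dose children with the same exponential time from dosing (true median 84 days), censored at day 168. Typical Kaplan-Meier medians in days, low/high:

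| Assumed lags in days (low; high) | From dosing | From study start |
|---|---|---|
| 0–200; 200–400 | 66 / 84 | 177 / 397 |
| 0–300; 300–800 | 67 / 85 | 234 / 686 |
| 0–400; 500–1200 | 67 / 84 | 291 / 1003 |

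The gap in the dosing column is a small-sample effect of n = 6. True medians of 56 and 112 days give the same pattern.

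**Do other readings rescue the text?**
- *Count Week 24 from study start as well.* Since 168 < 325, every child dosed under v5 or later would be censored before he was dosed.
- *Read the term as each child's own enrolment.* Screening can add up to 70 days (Protocol 5.3). Delayed-treatment controls would carry 24 weeks to 3 years of untreated time (Protocol 3.4), although the SAP version history says control-period data will not be used.

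**The case against.** The best reply is that the intended clock can be recovered. Both endpoints are labelled as at Week 24, Week 24 is dosing-based throughout the SAP, baseline is the last assessment before dosing (4.10.1), and control-period data are excluded. On this view the phrase is a slip, and a sensible programmer would start at dosing. That may well be the intent. But the text names a different origin, the protocol defines it, and no passage overrides it. Because the SAP names dosing explicitly for survival and shedding, the different wording here could be taken as deliberate.

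A second objection concerns the bound on the high-dose median, and it stands for the ≤16 h endpoint. That analysis is limited to invasively ventilated children, and Part 1 also admitted children on noninvasive support. With 8 Cohort 2 children and only 7 others, the floor would be 7/15 = 0.47, and a median before day 325 would be possible. Removing Cohort 2 children instead would raise the floor. The documents do not give the counts, so the bound suits the sitting curve only. The lag bounds of 325, 798 and 297 days do not depend on it.

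Third, the consequence is limited. There is no hypothesis testing, and ventilation hours by visit, sitting by visit and individual milestone timelines are also reported on the dosing clock. A careful reader might spot the distortion. That limits the severity but does not make the medians usable.

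**Conclusion.** The concern holds. As written, the Kaplan-Meier times for the ≤16 h and sitting endpoints include each child's lag from first consent to dosing. For any child dosed under v5 or later the lag is at least 325 days, and it exceeds that of any of the six Cohort 1 low-dose children by at least 297 days. Both figures are longer than the 168-day response window. They rest on the protocol's stated cutoff, sentinel rule and version dates, and on a child dosed under v5 having been dosed on or after its date. The high-dose median of at least 325 days further assumes that all 17 children are analysed and that those outside Cohort 2 were dosed under v5 or later.

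The severity is modest: this should be fixed, but it affects only one other-secondary and one exploratory descriptive summary in the SAP. The primary endpoint, the key secondary endpoint and SAP survival do not depend on it.

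**What to change.** In SAP 4.4.2.2.1 and SAP 4.5.1.2.1, replace the study start date with the date of AT132 dosing (Day 1) as time zero. Make the same change in Protocol 7.4.2.2.2, including for time to death, so that it agrees with SAP 4.4.2.2.8. The protocol change is for consistency, since Protocol section 7 makes the final SAP the analysis of record.

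The cost is one phrase in three places and one programming variable. The dosing date is already used for survival, and no new data are needed.
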